9.6.8 Antibody Formation

The incidence and percentages of subjects who develop anti-evolocumab antibodies (binding and neutralizing) at any time will be tabulated.

9.6.9 Neurologic examination

The incidence of abnormal neurologic findings overall and in each exam area will be summarized.

The neurologic examination includes assessments of motor, sensory, reflexes, coordination and gait. On the relevant eCRF, each area is described as normal or abnormal. Overall neurologic finding will be based on all 5 assessments. It will be defined as abnormal if any of these 5 assessments is abnormal.

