1.4 Other Safety

- To evaluate the incidence of abnormal neurological examination findings after 80 weeks of SC evolocumab added to standard of care in pediatric subjects 10 to 17 years of age with HeFH or HoFH
- To assess cognitive function, assessed using the change from baseline in the components of the Cogstate battery at each scheduled administration, after 80 weeks of SC evolocumab added to standard of care in pediatric subjects 10 to 17 years of age with HeFH or HoFH

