7.7.6 Physical and Neurologic Examination

Physical examination (at screening and EOS) should include a neurologic examination. The neurologic examination should include assessments of motor, sensory, reflexes, coordination and gait.

On the relevant eCRF, each area should be described as normal or abnormal, and if abnormal, details should be recorded, including whether there is worsening from baseline. Any clinically significant changes in the physical examination per the investigator's opinion should be recorded on the Adverse Event CRF.

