10.4.4 Other Safety Endpoints

All analysis of the other safety endpoints will use the FAS.

Laboratory Parameters

Selected safety laboratory parameters will be summarized using descriptive statistics.

Vital Signs

Vital signs will be summarized using descriptive statistics.

Neurologic examination

The incidence of abnormal neurologic findings overall and in each exam area will be summarized by treatment group.

Cogstate battery

Change from baseline score in the components of the Cogstate battery at each scheduled administration will be summarized using descriptive statistics.

Anti-evolocumab antibodies

The incidence and percentages of subjects who develop anti-evolocumab antibodies (binding and neutralizing) at any time will be tabulated.

ECG

Summaries over time and/or changes from baseline over time will be provided for all ECG parameters.

Subjects' maximum change from baseline in QTcF will be categorized and the number and percentage of subjects in each group will be summarized.

Subjects' maximum post baseline values will also be categorized and the number and percentage of subjects in each group will be summarized.

Approved

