Appendix A. Analytical Study Week Assignments

Selected endpoints will be summarized by scheduled study visits in descriptive analyses. Since the actual visits may not exactly coincide with their scheduled visit day, the actual visit day is mapped to the study visit generally by non-overlapping consecutive intervals covering the entire time continuum, with scheduled visit time being the center of each interval. The mapping intervals for all distinct schedules are summarized in the following tables.

Tests / Analytical Visit Window	Week 4	Week 12	Week 24	Week 36	Week 48	Week 60	Week 72	Week 80
Target day	29	85	169	253	337	421	505	561
Vital Signs (sitting BP, HR)	(1, 56]	(56, 126]	(126, 252]		(252, 448]			(448, EOS]
Physical exam (including neurologic examination)								(1, EOS]
Height, weight, cIMT ^a , Tanner staging			(1, 252]		(252, 448]			(448, EOS]
Neurocognitive assessment (Cogstate battery) - HoFH			(1, 252]		(252, 448]			(448, EOS]
Neurocognitive assessment (Cogstate battery) - HeFH			(1, 364]					(364, EOS]
12 lead ECG								(1, EOS]
Lipids		(1, 210]			(210, 448]			(448, EOS]
ApoA1, ApoB100, Lp(a)		(1, 322]						(322, EOS]
PK (evolocumab), PCSK9		(1, 322]						(322, EOS]
Chemistry, including glucose		(1, 210]			(210, 448]			(448, EOS]
Hematology					(1, 448]			(448, EOS]
Estradiol (females) / testosterone (males)								(1, EOS]
HbA1c, FSH, LH, ACTH, DHEA-S, cortisol, hsCRP, vitamins A/D/E/K								(1, EOS]
CK		(1, 210]			(210, 448]			(448, EOS]
Biomarkers (blood)								(1, EOS]
Anti-evolocumab antibodies								(1, EOS]
HCV viral load					(1, 448]			(448, EOS]
Urinalysis, urine microalbumin, urine creatinine, urine albumin/creatinine ratio								(1, EOS]

^a cIMT assessments conducted up to and including study day 28 are considered baseline values.

Handling multiple records assigned to an analytical study week:

If there is more than one record in a study week interval, the analytical record for that specific study week will be defined as the record closest to the scheduled visit day of that specific study week ($7 \times \text{study week} + 1$). If two records are equidistant from the scheduled day, then the earlier record will be chosen. If there are multiple records on the same day, the last record will be used.

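### The planned neurologic incidence in SAP 9.6.9 does not separate pre-existing from new or worsened abnormalities, so it reports the proportion abnormal at about week 80

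*SAP*

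**What the plan says.** The objective in Protocol Section 1.4 is "To evaluate the incidence of abnormal neurological examination findings after 80 weeks of SC evolocumab". For the analysis, Protocol Section 10.4.4 states: "The incidence of abnormal neurologic findings overall and in each exam area will be summarized by treatment group". SAP Section 9.6.9 repeats the summary ("The incidence of abnormal neurologic findings overall and in each exam area will be summarized") and adds how the five areas (motor, sensory, reflexes, coordination, gait) combine: "It will be defined as abnormal if any of these 5 assessments is abnormal".

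The two documents describe the data differently. The SAP says: "On the relevant eCRF, each area is described as normal or abnormal". Protocol Section 7.7.6 asks for more: "if abnormal, details should be recorded, including whether there is worsening from baseline".

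On timing, Protocol Section 7.7.6 says: "Physical examination (at screening and EOS) should include a neurologic examination". Table 2 marks the examination at HoFH screening and at week 80 only. SAP Appendix A maps all post-day-1 examinations to a single week 80 window, (1, EOS], and keeps the one record closest to the scheduled day.

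SAP Section 5.2 does define a baseline that would cover this variable. For de novo HoFH subjects it is the last non-missing value before first dose. For HeFH rollovers it is the parent-study baseline. Section 9.6.9 refers to neither.

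**The concern.** An incidence after treatment should count subjects who acquire or worsen a finding, among those who could. The rule in SAP 9.6.9 looks only at the post-baseline result. A stable abnormality that predates evolocumab scores the same as a new one. Worsening within an area that was already abnormal cannot be seen at all, because the area is abnormal at both times.

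The study is single-arm, so each subject's own baseline is the main reference. With one scheduled post-baseline examination, no sequence of visits can separate old findings from new ones either. A reader of the table could take pre-existing abnormalities for a drug signal, or miss a few new cases among the old ones. The protocol already asks sites for the item that would tell them apart.

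**Working it through.** **No figure to reproduce.** The documents give no neurologic rate, target or precision, and the study is descriptive. The first check is textual.

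**How the SAP treats other endpoints.**

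| Endpoint | SAP section | Reference to baseline or onset |
|---|---|---|
| Treatment-emergent adverse events | 5.3 | Onset on or after first dose |
| Tanner staging | 9.6.3 | Shift from baseline |
| hsCRP | 9.5.3 | Shift table, baseline to maximum post-baseline |
| ECG intervals | 9.6.7 | Change from baseline |
| Cogstate | 9.6.10 | Change from baseline |
| Neurologic examination | 9.6.9 | None |

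**Who is counted under the rule as written.**

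- Normal before, abnormal at week 80: counted.
- Abnormal before, still abnormal at week 80: counted.
- Abnormal before, normal at week 80: not counted, because Appendix A takes only the post-day-1 record.

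The result is therefore the proportion abnormal in the week 80 window.

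**Size, under assumed rates.** Let b be the proportion abnormal before evolocumab, s the share of those still abnormal at week 80, and q the new-onset proportion among subjects normal at baseline. All three are assumptions. Everyone is taken to be examined.

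- Reported proportion: p = b·s + (1 − b)·q
- Share of counted cases that are pre-existing: b·s / p

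| b | s | q | p | Pre-existing share |
|---|---|---|---|---|
| 1% | 50% | 1% | 0.0050 + 0.0099 = 1.49% | 34% |
| 1% | 50% | 2% | 0.0050 + 0.0198 = 2.48% | 20% |
| 2% | 100% | 1% | 0.0200 + 0.0098 = 2.98% | 67% |
| 5% | 100% | 1% | 0.0500 + 0.0095 = 5.95% | 84% |
| 5% | 100% | 2% | 0.0500 + 0.0190 = 6.90% | 72% |

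Over b = 1–5%, s = 50–100% and q = 1–2%, the reported figure runs from about 1.5% to 6.9%, and the pre-existing share from 20% to 84%. With q = 0 the table would still show b·s, that is 0.5% to 5.0%.

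In the middle row, with the planned total of about 124 subjects, the table would show about 124 × 0.0298 = 3.7 cases. Only 124 × 0.98 × 0.01 = 1.2 of them would be new.

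**Chance that the problem arises.** The probability of at least one subject abnormal before evolocumab is 1 − (1 − b)^n.

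| b | n = 124 | n = 10 (HoFH) |
|---|---|---|
| 1% | 71% | 10% |
| 2% | 92% | 18% |
| 5% | 99.8% | 40% |

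In the HoFH cohort, one such subject who remains abnormal gives 1/10 = 10%.

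**The case against.** The case on the other side has four parts.

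1. A reader might infer that every abnormal examination is counted, whenever it took place. The documents do not support that. Appendix A admits only post-day-1 records and keeps one per window, so a pre-dose abnormality that resolves drops out. Nor does the SAP expressly say that pre-existing findings count. The sentence quoted from 9.6.9 only combines five areas into one result. The point rests on the absence of any baseline condition, and it applies to persistent abnormalities.

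2. The SAP follows the protocol. The endpoint in Protocol Section 10.1.1.4 is abnormal examination findings, without the words new or worsened, and a week 80 proportion is a legitimate description of that. This stands as far as it goes. It leaves the word incidence wrong and the recorded worsening item unused.

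3. New deficits have another route. Protocol Section 7.7.6 sends clinically significant changes to the adverse event form, Section 9.1.1 treats worsening of a pre-existing condition as an adverse event, and treatment-emergent events carry an onset rule. A reader who concluded that a real deficit would be lost from the report would go too far. The route depends on the investigator's judgment of clinical significance, however, and it does not correct this table.

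4. The comparison may not be available for most subjects. Table 2 marks no pre-dose neurologic examination for HeFH rollovers in this study, and their baseline comes from the parent study. These documents do not show whether a comparable five-area examination was done there. This stands and shapes the fix.

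**Conclusion.** The point holds in this form: SAP 9.6.9 labels as incidence what is the proportion abnormal at about week 80, and it does not distinguish pre-existing from new or worsened findings. The size depends on rates that the documents do not give. The 1.5–6.9% range and the 20–84% pre-existing share are illustrations under the assumptions above. If no abnormality present before evolocumab persists to week 80, the reported count equals the count of new cases and the problem does not arise. The 10% in HoFH needs one persistent case among about 10 subjects.

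The importance is moderate to low. The endpoint is descriptive, is listed under other safety in the protocol and under exploratory in the SAP, and carries no test or stopping rule. It is still worth correcting, because the table could mislead in either direction.

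**What to change.** In SAP 9.6.9:

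- Report new abnormalities, overall and for each of the five areas: normal at baseline and abnormal post-baseline, with subjects normal at baseline as the denominator.
- Report worsened abnormalities from the eCRF worsening item, overall and per area.
- Add a baseline-to-week-80 normal/abnormal shift table by the three groups of SAP Section 5.3.
- Keep the existing summary, but label it as the proportion abnormal at week 80.
- State which parent-study examination supplies the baseline for the HeFH rollovers (about 111 subjects). The choice matters for those randomized to placebo: against the parent baseline, a finding that arose during the 24 placebo weeks would be classed as new. If no comparable parent examination exists, rely on the eCRF worsening item for that cohort and say so in the table.

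The cost is SAP wording, one extra table and a link to parent-study data. The protocol already requires the worsening item, so no new assessment is needed.

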9.6.10 Cogstate Battery

Change from baseline score in the components of the Cogstate battery at each scheduled administration will be summarized using descriptive statistics.

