3. EXPERIMENTAL PLAN

3.1 Study Design

This is an open-label, single-arm, multicenter study. Subjects are eligible for screening if they have completed Study 20120123 (and did not experience a treatment-related serious adverse event) or if they are 10 to 17 years of age at time of enrollment and have HoFH. The minimum expected enrollment of HeFH (rollover) subjects is approximately 70% of subjects enrolled in Study 20120123 or approximately **111** subjects. In addition, approximately 10 subjects with HoFH (and without prior participation in an evolocumab study) will be enrolled for an expected total enrollment of approximately **124** subjects. Depending on willingness of 20120123 subjects to continue evolocumab administration, final enrollment may be smaller or greater.

Where permitted by local regulations, the study includes collection of biomarker development samples and subjects will be invited to consent/assent to pharmacogenetic analyses.

The overall study design is described by a [study schema](#) at the end of the protocol synopsis section.

The study endpoints are defined in [Section 10.1.1](#).

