7.7.7 Cognitive Assessments (Cogstate Battery)

The Cogstate battery is a largely language-independent battery of neurologic tests administered via computer which has been validated for use in the age group to be studied in Study 20120124. The Cogstate battery has a significant normative database, and has been used in over 190 clinical trials to detect both enhancement and deterioration associated with drug effects. Subject performance on the Cogstate battery is also independent of education level, estimated intelligence quotient (IQ) and language or culture of origin (Yamashita et al, 2011; Yoshida et al, 2011; Boivin et al, 2010; Bangirana et al, 2009; Dingwall et al, 2009; Lim et al, 2009), allowing accurate classifications of cognitive dysfunction or cognitive change with reference only to a child's age and gender.

Cogstate tests have been used to examine the potential adverse effects of mobile telephone use in young adolescents (Abramson et al, 2009), adolescents with eating disorders (Allen et al, 2013), skipping breakfast in elementary school children (Kral et al, 2012), dietary patterns in adolescents (Nyaradi et al, 2014), and in utero exposure to cocaine (Mayes et al, 2007). The Cogstate tests have also been used to examine the cognitive effects of treatment with stimulant medication in children with ADHD ([Mollica et al, 2004]: eight to 12 year olds; [Snyder et al, 2008]: six to 16 year olds), as well as the effects of computerized cognitive rehabilitation in pediatric cerebral malaria survivors as young as five years old (Bangirana et al, 2009).

Additionally, regulatory authorities have approved the use of Cogstate tests for monitoring and evaluating the safety of CNS penetrant drugs in a range of pediatric indications, including epilepsy (NCT01389596), neurogenic detrusor over-activity (NCT01565694), bipolar depression (NCT02046369), schizophrenia (NCT01911429) and hyponatremia (NCT02012959) and in children as young as four years old. In sports, Cogstate tests are being used to make return-to-play decisions in suspected concussion.

In Study 20120124, the battery will consist of the following 4 tests:

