4.1 Planned Covariates

No planned covariates will be included in the analysis.

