4.2 Subgroups

No subgroup analysis will be included in the analysis.

5. Definitions

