5.2 Demographics and Baseline Related Definitions

Age at Enrollment

Age will be collected as the subject's age in years at enrollment as recorded on the eCRF.

Baseline Lipid and Lipid-related Parameters

For subjects with HeFH rolling over from parent study 20120123, baseline lipid and lipid-related parameters are defined as parent study baseline lipid and lipid-related parameters. For lipids (total cholesterol, HDL-C, LDL-C, VLDL-C and triglycerides), ApoA1, ApoB, hsCRP, Lp(a) and their derived parameters (eg, ratio between them) of de novo subjects with HoFH, the baseline values are defined as the mean of the two most recent non-missing concentrations measured through central lab prior to or on Study Day 1. If for any reason only 1 value is available, then that value will be used as baseline for de novo subjects.

Other Baseline Values

For subjects with HeFH rolling over from parent study 20120123, other baseline values (ECG, PCSK9, and other variables) are defined as parent study baseline values.

For de novo subjects with HoFH, the baseline ECG value is defined as the mean over all non-missing triplicate averages of 3 (or all available) readings from each set of triplicate taken prior to or on Study Day 1. For PCSK9, the baseline value is defined as the average of the last two non-missing values collected prior to first IP administration. If for any reason only 1 value is available, then that value will be used as baseline. For all other variables, the baseline value is defined as the last non-missing value collected prior to first IP administration.

Change (absolute change) from Baseline

The arithmetic difference between a post-baseline value and baseline for a given time point:

Change (absolute change) from baseline = (post-baseline value – baseline value)

Percent Change from Baseline

The percent change from baseline for a given variable at a given time point is defined as:

$100 \times [(value\ at\ given\ time\ point - baseline\ value) / baseline\ value]$

Baseline Metabolic Syndrome

For each subject without type 2 diabetes mellitus, metabolic syndrome is identified by the presence of 3 or more of the components listed below (modified AHA/NHLBI criteria, [Fryar et al 2012](#), [Ji et al 2010](#)). Subjects with type 2 diabetes cannot be categorized as having metabolic syndrome.

Age 10 to <16 years

Risk Factor	Defining Level
Elevated waist circumference:	Obesity > 90 percentile or adult cut-off if lower (refer to the cut-offs below)

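### Cogstate is summarised only as unadjusted change from baseline, with the score metric undefined, so in a single-arm adolescent study developmental gain could mask a decline

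*SAP*

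**What the plan says.** The whole Cogstate analysis is one sentence in SAP 9.6.10: "Change from baseline score in the components of the Cogstate battery at each scheduled administration will be summarized using descriptive statistics". Protocol 10.4.4 plans the same. SAP 5.2 defines change as "The arithmetic difference between a post-baseline value and baseline for a given time point". On adjustment, SAP 4.1 states "No planned covariates will be included in the analysis" and SAP 4.2 "No subgroup analysis will be included in the analysis". On design, Protocol 3.1 states "This is an open-label, single-arm, multicenter study".

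For HeFH rollover subjects, SAP 5.2 states that "other baseline values (ECG, PCSK9, and other variables) are defined as parent study baseline values". Table 2 of the protocol limits the day 1 Cogstate session to HoFH subjects, so HeFH subjects have no Cogstate baseline of their own in this study.

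Protocol 7.7.7 supports the choice of battery partly by its norms: "The Cogstate battery has a significant normative database", and performance is said to be independent of education, IQ, language and culture, "allowing accurate classifications of cognitive dysfunction or cognitive change with reference only to" the child's age and gender.

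Neither document specifies a standardised score, a comparison with norms, a practice correction or a threshold for individual decline.

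**The concern.** Assessing cognition is a stated safety objective (Protocol 1.4). Protocol 2.4 explains why: development is still under way at these ages. That same fact makes unadjusted change hard to read. In one treated group, observed change is the sum of maturation, practice and any drug effect, and nothing in the planned summary separates them. If scores improve with age, a drug-related decrement of similar size would appear as stability. The error would then run towards a finding of no harm, which is the wrong direction for a safety measure.

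The protocol names the reference that would help, age and gender norms, but the analysis text does not use it.

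**Working it through.** **Is there a plan figure to reproduce?** No. The documents give no SD, effect size or threshold for Cogstate. The check is therefore of the text, followed by an illustration.

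**Time covered by the change score**
- HoFH, day 1 to week 80: 80 × 7 / 365.25 = 1.53 years.
- HeFH, parent-study baseline to week 80: the parent study lasts 24 weeks (Protocol 2.4), so (24 + 80) × 7 / 365.25 = 1.99 years. This assumes no gap at rollover and a Cogstate session at the parent-study baseline.
- SAP Appendix A maps HeFH Cogstate records from day 365 onwards to week 80. A record at the start of that window has an elapsed time of (24 × 7 + 364) / 365.25 = 1.46 years. Records labelled week 80 can therefore span about 1.5 to 2.0 years of development.

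**What could remove maturation?**

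| Feature | Where | Effect |
|---|---|---|
| Practice session for HoFH | Protocol 7.7.7 | Reduces practice effects only; about 10 subjects |
| 20 alternate maze pathways | Protocol 7.7.7 | Reduces practice effects only; one of four tests |
| Reporting by parent-study arm | SAP 5.3 | Both arms receive evolocumab here; not an untreated control |
| Neurocognitive adverse events | SAP 9.6.2 | Reported events, not test performance |
| Covariates, subgroups | SAP 4.1, 4.2 | None planned |

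None of these corrects the change score for development.

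**Illustration, in units of the baseline SD, with higher scores taken as better.** Assumptions not in the documents: a gain of 0.1 to 0.3 SD per year and an SD of change of 0.7 to 1.0.

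Mean unadjusted change = (gain per year × years) − decline. The decline that would show as zero change is therefore gain × years:
- HoFH: 0.1 × 1.53 = 0.15 to 0.3 × 1.53 = 0.46 SD.
- HeFH: 0.1 × 1.99 = 0.20 to 0.3 × 1.99 = 0.60 SD.

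One worked case has a gain of 0.2 SD per year and a true decline of 0.3 SD, with SE = SD of change / √n:
- HeFH, n = 111: unadjusted mean 0.2 × 1.99 − 0.3 = +0.10 SD; norm-referenced mean −0.30 SD. SE is 0.7/√111 = 0.066 to 1.0/√111 = 0.095, so the norm-referenced mean lies 3.2 to 4.5 SE below zero.
- HeFH, share of subjects below −1.645 SD of change: 3.7% to 4.1% unadjusted against 8.9% to 11.2% norm-referenced, where 5% is expected with no effect.
- HoFH, n = 10: unadjusted mean 0.2 × 1.53 − 0.3 = +0.01 SD; norm-referenced mean −0.30 SD. SE is 0.7/√10 = 0.22 to 1.0/√10 = 0.32, so even the norm-referenced mean is imprecise.

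**Chance rate for a simple count of decliners.** Suppose decline is counted as a fall of at least 1 SD. With normal changes and no drug effect, the share crossing is Φ(−1/0.7) = 7.7% to Φ(−1/1.0) = 15.9%. That is about 8 to 18 of 111 HeFH subjects for each of four components. Such a count cannot be read without its expected rate.

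**The case against.** The strongest reply is that a reader might infer from the SAP that raw scores are analysed, and the documents do not say so. They refer only to the component score. A difference between two standardised scores is also an arithmetic difference, and the absence of covariates says nothing about how a score is derived. Protocol 7.7.7 is compatible with scores that are already referenced to age. This stands: what the text supports is that the metric is unspecified and that no norm-referenced summary is written down.

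A reader might also infer that the SAP departs from the protocol. It does not. The objective, the endpoint and Protocol 10.4.4 all prescribe change in the components. The measure is not a leading one either: the protocol lists it among other safety endpoints, the SAP lists it under exploratory, and the whole study is descriptive. That limits the weight of the point. A descriptive summary still needs a metric that can be interpreted.

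The parent-study arms do offer a partial contrast, since maturation and practice should be similar in both. But they differ only by 24 weeks of earlier treatment, so an effect that both arms acquire during this study would not show between them.

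Neurocognitive events, neurological examination and an external monitoring committee mean that Cogstate is not the only safeguard. None of them makes the change score easier to read.

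Finally, age norms address maturation, not clearly practice. The documents do not say whether the norms cover retesting. That stands and limits what the fix can achieve.

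**Conclusion.** The point holds in a conditional form. SAP 9.6.10 leaves the score undefined and plans only unadjusted change, over 80 weeks in HoFH and about 104 weeks in HeFH subjects, without a control arm. If the component scores are already age-normed, the SAP needs only to say so. If they are not, developmental gain is mixed with any drug effect and could mask a decline.

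A reader might go further and conclude that the analysis is biased towards no harm by a known amount. The documents do not support that. They give no rate of cognitive gain, and the offsets of 0.15 to 0.46 SD and 0.20 to 0.60 SD are simply an assumed 0.1 to 0.3 SD per year multiplied by elapsed time. They show what is possible, not what will occur.

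This is a cheap improvement to a stated safety objective. It is not a flaw in the primary analysis. The practical gain is mainly for the roughly 111 HeFH subjects.

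**What to change.** In SAP 9.6.10:

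1. For each of the four components, name the score analysed, state whether it is age-referenced, and state which direction is better. Direction needs stating because the maze task records errors and two of the tests are reaction-time tasks.
2. Beside the planned change score, summarise change in the age- and sex-standardised z-score, normed at the age of testing, from the normative database cited in Protocol 7.7.7.
3. If individual decline is counted, pre-specify a reliable-change threshold and print the proportion expected by chance next to the observed one.
4. State that norms may not remove practice effects.

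The cost is SAP wording and one derived variable per component; no new visits or data collection are needed. The downside is that norms must cover every age tested, including subjects who pass 17 on study. Inclusion criterion 104 admits HoFH subjects up to the day before their 18th birthday, so one could be about 18 + 1.53 = 19.5 years old at week 80. HoFH summaries, on about 10 subjects, will stay imprecise whichever score is used.
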